4.4.4. Selection of Doses in the Study

Subjects in Groups 1, 2, and 3 are to receive a first vaccination of AS03 adjuvanted 2013 A/H7N9 IIV at HA dose of 3.75mcg, and a second vaccination of either AS03 adjuvanted 2017 A/H7N9 IIV at HA dose of 3.75mcg (Groups 1 and 2) or unadjuvanted 2017 A/H7N9 IIV at HA dose of 15mcg (Group 3). Subjects in Groups 4, 5 are to receive two AS03 adjuvanted 2017 A/H7N9 vaccinations at HA doses of 3.75. Subjects in Group 6 are to receive a first vaccination of AS03 adjuvanted 2017 A/H7N9 IIV at HA dose of 3.75mcg, and a second vaccination of unadjuvanted 2017 A/H7N9 IIV at HA dose of 15mcg.

The 3.75 mcg with AS03 dose was selected to evaluate safety and immunogenicity of antigen sparing dose strategies compared to that of using a higher dose of 15 mcg without adjuvant. Using the 2013 and 2017 A/H7N9 IIVs allows the evaluation of priming effects of different A/H7N9 IIVs.

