9.1 Overall Study Design and Plan Description

Table 1: Study Design

| Influenza A/H7 Vaccine/Infection Naïve Subjects (Total N=180) | | Study Group/N | 1 st Study Vaccination Day 1 | 2 nd Study Vaccination ~ Day 22 post Vaccination 1 | 2 nd Study Vaccination ~ Day 121 post Vaccination 1 |
|---|-----------------------------|------------------|--|--|--|
| Study Vaccination Schedule | Heterologous Prime-Boost | 1/30 | 2013 A/H7N9 IIV 3.75 mcg + AS03 | 2017 A/H7N9 IIV 3.75 mcg + AS03 | |
| | | 2/30 | 2013 A/H7N9 IIV 3.75 mcg + AS03 | | 2017 A/H7N9 IIV 3.75 mcg + AS03 |
| | | 3/30 | 2013 A/H7N9 IIV 3.75 mcg + AS03 | | 2017 A/H7N9 IIV 15 mcg |
| | Homologous Prime-Boost | 4/30 | 2017 A/H7N9 IIV 3.75 mcg + AS03 | 2017 A/H7N9 IIV 3.75 mcg + AS03 | |
| | | 5/30 | 2017 A/H7N9 IIV 3.75 mcg + AS03 | | 2017 A/H7N9 IIV 3.75 mcg + AS03 |
| | | 6/30 | 2017 A/H7N9 IIV 3.75 mcg + AS03 | | 2017 A/H7N9 IIV 15 mcg |

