Tables with similar format:

- Table 57:** Summary of Hemagglutination Inhibition Antibody Against A/Shanghai/2/2013 (A/H7N9) by Study Group and Prior Seasonal Influenza Vaccination at 180 Days Post Second Vaccination, Per Protocol Population
- Table 58:** Summary of Neutralizing Antibody Against A/Shanghai/2/2013 (A/H7N9) by Study Group and Prior Seasonal Influenza Vaccination at 21 Days Post Second Vaccination, Per Protocol Population
- Table 59:** Summary of Neutralizing Antibody Against A/Shanghai/2/2013 (A/H7N9) by Study Group and Prior Seasonal Influenza Vaccination at 180 Days Post Second Vaccination, Per Protocol Population
- Table 60:** Summary of Hemagglutination Inhibition Antibody Against A/Hong Kong/125/2017 (A/H7N9) by Study Group and Prior Seasonal Influenza Vaccination at 21 Days Post Second Vaccination, Per Protocol Population
- Table 61:** Summary of Hemagglutination Inhibition Antibody Against A/Hong Kong/125/2017 (A/H7N9) by Study Group and Prior Seasonal Influenza Vaccination at 180 Days Post Second Vaccination, Per Protocol Population
- Table 62:** Summary of Neutralizing Antibody Against A/Hong Kong/125/2017 (A/H7N9) by Study Group and Prior Seasonal Influenza Vaccination at 21 Days Post Second Vaccination, Per Protocol Population
- Table 63:** Summary of Neutralizing Antibody Against A/Hong Kong/125/2017 (A/H7N9) by Study Group and Prior Seasonal Influenza Vaccination at 180 Days Second Vaccination, Per Protocol Population

Table 64: Logistic Regression Model to Evaluate the Relationship of Administration Schedule with HAI Seroconversion Against A/H7N9 Strains at 21 Days Post Second Study Vaccination, Per Protocol Population

[Implementation Note: Two- and three-way interaction terms will be included in the model at first. If interactions are not significant, fit final model in this table without interaction, and add footnote in table “No interaction terms were significant.”]

| Model Parameter | Parameter Category | A/Shanghai/2/2013 (A/H7N9) | | | | | A/Hong Kong/125/2017 (A/H7N9) | | | | |
|-----------------|------------------------|----------------------------|-------|---------|------------|-----------|-------------------------------|-------|---------|------------|-----------|
| | | Parameter Estimate | SE | p-value | Odds Ratio | 95%CI | Parameter Estimate | SE | p-value | Odds Ratio | 95%CI |
| Intercept | N/A | xxx.x | xxx.x | x.xxx | - | - | xxx.x | xxx.x | x.xxx | - | - |

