| Prime-boost | Homologous (reference) | - | - | - | - | - | - | - | - | - | - |
| | Heterologous | xxx.x | xxx.x | x.xxx | xx.x | xx.x-xx.x | xxx.x | xxx.x | x.xxx | xx.x | xx.x-xx.x |
| Boost Dose | 15 mcg (reference) | - | - | - | - | - | - | - | - | - | - |
| | 3.75 mcg + AS03 | xxx.x | xxx.x | x.xxx | xx.x | xx.x-xx.x | xxx.x | xxx.x | x.xxx | xx.x | xx.x-xx.x |
| Interval | 21 days (reference) | - | - | - | - | - | - | - | - | - | - |
| | 120 days | xxx.x | xxx.x | x.xxx | xx.x | xx.x-xx.x | xxx.x | xxx.x | x.xxx | xx.x | xx.x-xx.x |

n= XX (number of subjects with results available at 21 days post second study vaccination in the Per Protocol Population.)
XX subjects missing covariate data were excluded from this analysis.
SE = Standard Error.

Tables with similar format

Table 65: Logistic Regression Model to Evaluate the Relationship of Administration Schedule with HAI Seroconversion Against A/H7N9 Strains at 180 Days Post Second Study Vaccination, Per Protocol Population

Table 66: Logistic Regression Model to Evaluate the Relationship of Administration Schedule with Neut Seroconversion Against A/H7N9 Strains at 21 Days Post Second Study Vaccination, Per Protocol Population

Table 67: Logistic Regression Model to Evaluate the Relationship of Administration Schedule with Neut Seroconversion Against A/H7N9 Strains at 180 Days Post Second Study Vaccination, Per Protocol Population

Table 68: Logistic Regression Model to Evaluate the Relationship of Administration Schedule with HAI Seroconversion Against A/H7N9 Strains at 21 Days Post Second Study Vaccination, Adjusted for Baseline Covariates, Per Protocol Population (N=X)

| Model Parameter | Parameter Category | A/Shanghai/2/2013 (A/H7N9) | | | | | A/Hong Kong/125/2017 (A/H7N9) | | | | |
|--|---|----------------------------|-------|---------|------------|-----------|-------------------------------|-------|---------|------------|-----------|
| | | Parameter Estimate | SE | p-value | Odds Ratio | 95%CI | Parameter Estimate | SE | p-value | Odds Ratio | 95%CI |
| Intercept | N/A | xxx.x | xxx.x | x.xxx | - | - | xxx.x | xxx.x | x.xxx | - | - |
| Prime-boost | Homologous (reference) | - | - | - | - | - | - | - | - | - | - |
| | Heterologous | xxx.x | xxx.x | x.xxx | xx.x | xx.x-xx.x | xxx.x | xxx.x | x.xxx | xx.x | xx.x-xx.x |
| Boost Dose | 15 mcg (reference) | - | - | - | - | - | - | - | - | - | - |

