Table 69: Logistic Regression Model to Evaluate the Relationship of Administration Schedule with HAI Seroconversion Against A/H7N9 Strains at 180 Days Post Second Study Vaccination, Adjusted for Baseline Covariates, Per Protocol Population

Table 70: Logistic Regression Model to Evaluate the Relationship of Administration Schedule with Neut Seroconversion Against A/H7N9 Strains at 21 Days Post Second Study Vaccination, Adjusted for Baseline Covariates, Per Protocol Population

Table 71: Logistic Regression Model to Evaluate the Relationship of Administration Schedule with Neut Seroconversion Against A/H7N9 Strains at 180 Days Post Second Study Vaccination, Adjusted for Baseline Covariates, Per Protocol Population

Table 72: Multiple Linear Regression Model to Evaluate the Relationship of Administration Schedule with Log-Adjusted HAI Titer Against A/H7N9 Strains at 21 Days Post Second Study Vaccination, Per Protocol Population (N=X)

| Model Parameter | Parameter Category | A/Shanghai/2/2013 (A/H7N9) | | | | A/Hong Kong/125/2017 (A/H7N9) | | | |
|-----------------|------------------------|----------------------------|-------|-------|---------|-------------------------------|-------|-------|---------|
| | | Parameter Estimate | SE | 95%CI | p-value | Parameter Estimate | SE | 95%CI | p-value |
| Intercept | N/A | xxx.x | xxx.x | x.xxx | x.xxx | xxx.x | xxx.x | x.xxx | x.xxx |
| Prime-boost | Homologous (reference) | - | - | - | - | - | - | - | - |
| | Heterologous | xxx.x | xxx.x | x.xxx | xx.x | xxx.x | xxx.x | x.xxx | xx.x |
| Boost Dose | 15 mcg (reference) | - | - | - | - | - | - | - | - |
| | 3.75 mcg + AS03 | xxx.x | xxx.x | x.xxx | xx.x | xxx.x | xxx.x | x.xxx | xx.x |
| Interval | 21 days (reference) | - | - | - | - | - | - | - | - |
| | 120 days | xxx.x | xxx.x | x.xxx | xx.x | xxx.x | xxx.x | x.xxx | xx.x |

n = XX (number of subjects with results available at 21 days post second study vaccination in the Per Protocol Population).
XX subjects missing covariate data were excluded from this analysis.
SE = Standard Error.

Tables with similar format:

Table 73: Multiple Linear Regression Model to Evaluate the Relationship of Administration Schedule with Log-Adjusted HAI Titer Against A/H7N9 Strains at 180 Days Post Second Study Vaccination, Per Protocol Population

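### The Table 64 note and SAP 8.3.2 disagree on dropping interactions; if interactions are kept with the shells' reference levels, the Heterologous row describes a schedule no arm received

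*SAP*

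**What the plan says.** SAP 8.3.2 defines three binary factors: PrimeBoost (homologous, heterologous), BoostDose (3.75 mcg+AS03, 15 mcg) and Interval (21, 120 days). Each of Models 1A to 2B has the three main effects plus PrimeBoost×BoostDose and PrimeBoost×Interval. There is no BoostDose×Interval term, no three-way term and no rule for removing interactions. SAP 9.3.1 repeats this equation for solicited events (Tables 87–88).

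The implementation note above Table 64 (SAP Appendix 1) says something else: "Two- and three-way interaction terms will be included in the model at first". It continues: "If interactions are not significant, fit final model in this table without interaction", with the footnote "No interaction terms were significant". Tables 65–67 share that format. The shells for Tables 68, 72 ("Multiple Linear Regression Model to Evaluate the Relationship of Administration Schedule with Log-Adjusted HAI Titer"), 76 and 87 carry no such instruction, although 8.3.2 says that all its models have a similar structure.

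All these shells mark homologous, 15 mcg and 21 days as reference levels and list main-effect rows (plus covariates in Tables 68 and 76). None has an interaction row.

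On the design, SAP 4.4.4 gives Groups 3 and 6 "a second vaccination of unadjuvanted 2017 A/H7N9 IIV at HA dose of 15mcg". In SAP Table 1 the entry "2017 A/H7N9 IIV 15 mcg" appears only in the Day 121 column.

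**The concern.** Two analysts could follow this SAP and print different results under the same row label. One keeps the 8.3.2 interactions; the other tests them and usually drops them. The label Heterologous then stands either for a pooled prime effect or for a prime effect at 15 mcg and 21 days, which nobody received. The printed table has no interaction row to show which one it is.

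The priming effect of the two vaccines is a stated goal of the trial (SAP 2). These are the only planned between-arm models of seroconversion and log titer, and SAP 8.1 points to them. The Heterologous row and its p-value will therefore be read as the prime-strain result. In Tables 87–88 a p-value below 0.05 also triggers a further model for each individual event.

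**Working it through.** 1. **The plan's own figure.** SAP Table 8 assumes n = 30 − 3 = 27 per arm, a two-sided likelihood ratio test, alpha 0.05 and 80% power. Exact binomial enumeration of its five pairs gives 81.6, 79.4, 80.5, 81.3 and 80.1%. The table reproduces. It is used below only as a source of n and effect sizes.

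2. **Design (SAP Table 1).** Code PB = 1 for heterologous, BD = 1 for 3.75 mcg+AS03 and I = 1 for 120 days, so that zeros are the shells' references. The arms (PB, BD, I) are G1 (1,1,0), G2 (1,1,1), G3 (1,0,1), G4 (0,1,0), G5 (0,1,1), G6 (0,0,1). Neither (1,0,0) nor (0,0,0) exists.

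3. **Estimability.** In all six arms BD·I = BD + I − 1, and PB·BD·I = PB·BD + PB·I − PB. The main-effects model has 4 columns and rank 4. The 8.3.2 model has 6 columns and rank 6. The note's full model has 8 columns and rank 6. The two extra terms add no degrees of freedom; if software sets them to zero, the fit is that of 8.3.2.

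4. **What the rows estimate** (log titer or log odds, G = arm value). Solving the six-parameter model gives:
   - intercept = G4 − G5 + G6
   - Heterologous = (G1 − G4) − (G2 − G5) + (G3 − G6)
   - BoostDose = G5 − G6; Interval = G5 − G4

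   The first two refer to the empty cell; the last two are observed contrasts. With interactions dropped, Heterologous = [(G1 − G4) + (G2 − G5) + (G3 − G6)]/3. This is exact for log titer with equal arms and approximate for log odds.

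5. **Precision on log titer.** SE = SD × √(f/27), where f is the sum of squared arm weights. Differences detectable with 80% power use the noncentral t with 156 df.

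| Row | f | SE (SD units) | Detectable difference (SD units) |
|---|---|---|---|
| Kept, shell references | 6 | 0.471 | 1.33 |
| One arm pair | 2 | 0.272 | 0.77 |
| Pooled | 0.667 | 0.157 | 0.44 |

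   Ratios: 0.471/0.272 = 1.73 and 0.471/0.157 = 3.0.

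6. **8.3.2 followed literally, uniform prime effect** (4,000 simulated trials per pair, n = 27, 1-df likelihood ratio test; trials with an empty or full arm excluded, at most 123 per pair):

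| Homologous / heterologous | Kept row power | One pair | Pooled | Kept row opposite in sign to pooled |
|---|---|---|---|---|
| 0.20 / 0.55 | 31.4% | 79.5% | 99.8% | 7.4% |
| 0.30 / 0.68 | 35.9% | 80.1% | 99.9% | 6.6% |
| 0.40 / 0.77 | 33.9% | 82.8% | 99.9% | 6.4% |
| 0.50 / 0.84 | 32.7% | 79.1% | 99.8% | 7.0% |

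   Table 8's first pair (0.10/0.42) is left out. At 10% response an arm of 27 has no responders with probability 0.9^27 = 0.058, so at least one of three such arms is empty in 1 − 0.942³ ≈ 16% of trials.

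7. **Table 64 note followed, same four pairs** (8,000 trials each). Interactions are kept in 4.7–5.9% (joint test) or 7–10% (either term at 0.05; the note does not say which). A kept row of opposite sign occurs in 1.1–1.8% or 2.5–3.5%. A kept, opposite-sign row with p<0.05 occurs in 0.01–0.06%.

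8. **Table 64 note followed, one arm deviating** (assumption: all other arms at 50%). With Group 2 at 30%, the pair odds ratios are 1.0, 0.43 and 1.0, while the kept row targets 1.0 × 1.0/0.43 = 2.33. At 70% the figures are 1.0, 2.33, 1.0 and 0.43. Interactions are kept in 19–20% (joint) or 28–30% (either term), and a kept, opposite-sign row with p<0.05 occurs in 9–10%. With the same deviation in Group 1 or Group 3, that event occurs in 0.9–1.3%. With all arms equal (50% or 30%) it occurs in about 1%.

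**The case against.** The strongest reply is that the harm is conditional. It needs interactions to be kept, the shells' references to be carried into the interaction model, and the result to be printed in a main-effects layout. The Table 64 shell fits the case its note provides for, with interactions dropped. A kept version would lack the footnote, and a sensible programmer might add the missing rows. Under the note, the six-parameter fit survives in only about 5–10% of trials with a uniform effect. The analysis is exploratory, no formal hypothesis is tested, and the by-arm summaries with confidence intervals (Tables 24, 26, 28 and 30) let a reader compare matched arms directly.

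Most of this stands and limits the size of the point. It does not remove the defect. Equations and note still conflict on dropping interactions, Tables 68, 72, 76 and 87 state no rule at all, and no shell shows what to print when interactions stay. The Tables 87–88 trigger is a minor consequence, since it only adds per-event models.

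A reader might also infer that the note's full model breaks the analysis. It does not: the aliased terms add no degrees of freedom, and zeroing them returns the 8.3.2 fit.

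**Conclusion.** The point holds and should be corrected, as an inconsistency in exploratory modelling. SAP 8.3.2 and the Table 64 note give different results whenever interactions are dropped. When they are kept with the shells' references, the Heterologous row is an extrapolation to an unobserved cell, with SE 1.73 times one arm pair and 3.0 times the pooled effect. Under literal 8.3.2 and a uniform effect, this costs power (about 31–36% against over 99%) and gives the opposite sign in about 6–7% of trials.

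These figures assume 27 per arm, equal arms and reference-cell coding as printed in the shells. Carrying that coding into the interaction model is an inference, because the SAP states no other.

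Two stronger readings are not supported. First, a significant prime result of the wrong sign is not a likely product of the Table 64 note: it occurs in at most 0.06% with uniform effects. It reaches 9–10% only if Group 2 alone deviates, an illustrative assumption that suits the row's negative weight on G2−G5. Second, the primary immunogenicity results are not compromised: they are by-arm summaries that do not use these models (SAP 8 and 8.1), and Protocol 11.6.3 calls the models exploratory.

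**What to change.** - Delete BoostDose×Interval and the three-way term from the Table 64 note.
- State one model and one rule on interactions, including the test that decides significance if a drop rule is kept, for Tables 64–79 and 87–88.
- Use an observed reference cell (for example homologous, 3.75 mcg+AS03, 120 days, which is Group 5, so that the Heterologous row becomes G2−G5) or a six-level arm factor.
- Print the two PrimeBoost interaction rows whenever they are in the model.
- SAP 8.3.2 lists Day 22 post vaccination 1, but Tables 64–79 have no shell for it. BoostDose and Interval cannot act before the boost, so either fit prime strain only (Groups 1–3 v 4–6) or delete the time point.

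Reporting the three matched prime differences (G1−G4, G2−G5, G3−G6) and their mean would help readers but is optional.

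As a separate editorial item, SAP 6.1 lists Group 4's second vaccination as the 2013 vaccine and SAP Table 1 lists it as the 2017 vaccine; the two must be reconciled.

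The cost is SAP and shell wording and a few contrast statements, with no new data, subjects or protocol change.

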15. Have been hospitalized for psychiatric illness, history of suicide attempt, or confinement for danger to self or others within 10 years prior to study vaccination.
16. Have taken oral or parenteral (including intra-articular) corticosteroids of any dose within 30 days prior to study vaccination.
17. Have taken high-dose inhaled corticosteroids⁸ within 30 days prior to each study vaccination.

⁸High-dose defined as per age as using inhaled high-dose per reference chart in the National Heart, Lung and Blood Institute Guidelines for the Diagnosis and Management of Asthma (EPR-3) or other lists published in UPTODATE.

18. Received a licensed, live vaccine within 30 days prior to the first study vaccination, or plan to receive a licensed, live vaccine within 30 days before or after each study vaccination.
19. Received or plan to receive a licensed, inactivated vaccine (excluding all licensed, seasonal IIVs) within 14 days before or after each study vaccination.
20. Received or plan to receive a licensed, seasonal IIV within 21 days before or after each study vaccination.
21. Received immunoglobulin or other blood products (except Rho D immunoglobulin) within 90 days prior to each study vaccination.
22. Received an experimental agent⁹ within 30 days prior to the first study vaccination or expect to receive an experimental agent¹⁰ during the trial-reporting period¹¹.

⁹Including vaccine, drug, biologic, device, blood product, or medication.

¹⁰Other than from participation in this trial.

¹¹Approximately 12 months after the last study vaccination.

23. Are participating or plan to participate in another clinical trial with an interventional agent¹² that will be received during the trial-reporting period¹³.

¹²Including licensed or unlicensed vaccine, drug, biologic, device, blood product, or medication.

¹³Approximately 12 months after the last study vaccination.

24. Received or plan to receive an influenza A/H7 vaccine¹⁴ or have a history of influenza A/H7 subtype infection.

¹⁴And assigned to a treatment arm receiving influenza A/H7 vaccine, i.e., does not apply to documented placebo recipients.

25. Had substantial direct contact¹⁵ with live or freshly slaughtered poultry or pigeons while in mainland China within the past five years.

¹⁵Substantial direct contact is defined as visited a poultry farm and/or a live poultry market.

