4.4.5. Selection and Timing of Dose for Each Subject

Each subject is to be randomly assigned to a study group which will define the number and timing of 2013 and/or 2017 A/H7N9 vaccinations. The first vaccination for all subjects takes place on the day of randomization and will include vaccination with AS03 adjuvanted 2013 A/H7N9 IIV (Groups 1,2,3) or AS03 adjuvanted 2017 A/H7N9 IIV (Groups 4,5,6). The second vaccination of 2017 A/H7N9 IIV takes place approximately 21 days after the first vaccination for Groups 1 and 4 (protocol defined window of 21-28 days post first vaccination), and approximately 120 days after the first vaccination for Groups 2, 3, 5, and 6 (protocol defined window of 113-134 days post first vaccination).

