6.4. Covariates and Subgroups

As a protocol defined exploratory analysis, HAI antibody response following the second vaccination will be summarized stratified by the following covariates: age (categorical: 19-34, 35-50), sex (male, female), body mass index (<30, ≥30), and prior receipt of seasonal influenza vaccine(s). Prior receipt of influenza vaccines, including any reported prior receipt of A/H5 vaccinations, or reported seasonal vaccination receipt will also be included as covariates. Summaries of prior seasonal vaccination will include breakdowns of receipt of the two seasonal vaccinations prior to study initiation (did not receive 2016-2017 or 2018-2019; received 2016-2017 and/or 2018-2019) as well as independently assessing subject receipt of 2018-2019 seasonal vaccine (did not receive/received) prior to the second dose of study vaccine. These covariates will be considered in statistical modeling as described in Section 8.3. As these analyses are exploratory, the study was not powered for any subgroup analyses.

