9.1. Demographic and Other Baseline Characteristics

Summaries of age, sex, ethnicity, race, BMI, and prior receipt of seasonal influenza vaccine will be presented by site ([Table 19](#), [Table 20](#)) and by study group ([Table 21](#), [Table 22](#)). Age will be summarized as a continuous variable. Ethnicity is categorized as Hispanic or Latino, or not Hispanic and not Latino. In accordance with NIH reporting policy, subjects may self-designate as belonging to more than one race or may refuse to identify a race, the latter reflected in the electronic case report form (eCRF) as “No” to each racial option. BMI will be summarized as a continuous as well as categorical variable, categorized as (<30, ≥30). Self-reported history of prior receipt of influenza vaccines will be broken down by the following categories: receipt of seasonal vaccines for prior seasons (2016-2017, 2017-2018), receipt of seasonal vaccine for the current season (2018-2019; considered up to receipt of study dose 2), and receipt of any A/H5 vaccines prior to enrollment. Demographic information for individual subjects will be provided in [Listing 6](#). Subjects’ prior influenza vaccination history (seasonal and non-seasonal) will be provided in [Listing 8](#).

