| | 3.75 mcg + AS03 | xxx.x | xxx.x | x.xxx | xx.x | xx.x-xx.x | xxx.x | xxx.x | x.xxx | xx.x | xx.x-xx.x |
| Interval | 21 days (reference) | - | - | - | - | - | - | - | - | - | - |
| | 120 days | xxx.x | xxx.x | x.xxx | xx.x | xx.x-xx.x | xxx.x | xxx.x | x.xxx | xx.x | xx.x-xx.x |
| Age (years) | N/A | xxx.x | xxx.x | x.xxx | xx.x | xx.x-xx.x | xxx.x | xxx.x | x.xxx | xx.x | xx.x-xx.x |
| Sex | Female (reference) | - | - | - | - | - | - | - | - | - | - |
| | Male | xxx.x | xxx.x | x.xxx | xx.x | xx.x-xx.x | xxx.x | xxx.x | x.xxx | xx.x | xx.x-xx.x |
| BMI | <30 (reference) | - | - | - | - | - | - | - | - | - | - |
| | ≥30 | xxx.x | xxx.x | x.xxx | xx.x | xx.x-xx.x | xxx.x | xxx.x | x.xxx | xx.x | xx.x-xx.x |
| Prior Receipt of Influenza Vaccine (Prior Seasons) | Did Not Receive 2016-2017 or 2017-2018 Seasonal Influenza Vaccination (reference) | - | - | - | - | - | - | - | - | - | - |
| | Received 2016-2017 and/or 2017-2018 Seasonal Influenza Vaccination | xxx.x | xxx.x | x.xxx | xx.x | xx.x-xx.x | xxx.x | xxx.x | x.xxx | xx.x | xx.x-xx.x |

| Model Parameter | Parameter Category | A/Shanghai/2/2013 (A/H7N9) | | | | | A/Hong Kong/125/2017 (A/H7N9) | | | | |
|--|--|----------------------------|-------|---------|------------|-----------|-------------------------------|-------|---------|------------|-----------|
| | | Parameter Estimate | SE | p-value | Odds Ratio | 95%CI | Parameter Estimate | SE | p-value | Odds Ratio | 95%CI |
| Receipt of Influenza Vaccine (Concurrent Season) | Did Not Receive 2018-2019 Seasonal Influenza Vaccine (reference) | - | - | - | - | - | - | - | - | - | - |
| | Received 2018-2019 Seasonal Influenza Vaccine (reference) | xxx.x | xxx.x | x.xxx | xx.x | xx.x-xx.x | xxx.x | xxx.x | x.xxx | xx.x | xx.x-xx.x |
| Prior Receipt of H5 Influenza Vaccine | No Prior H5 Influenza Vaccinations | - | - | - | - | - | - | - | - | - | - |
| | Received Prior H5 Influenza Vaccinations | xxx.x | xxx.x | x.xxx | xx.x | xx.x-xx.x | xxx.x | xxx.x | x.xxx | xx.x | xx.x-xx.x |

Note: Receipt of 2018-2019 vaccine is counted at any timepoint prior to receipt of the second study vaccination.
n= XX (number of subjects with results available at 21 days post second study vaccination in the Per Protocol Population).
XX subjects missing covariate data were excluded from this analysis.
SE = Standard Error.

Tables with similar format:

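### The 2018-2019 seasonal vaccine covariate in Models 1B and 2B is counted up to dose 2, so it is not a baseline variable and its window depends on the randomised interval

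*SAP*

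**What the plan says.** SAP 8.3.2 fits each regression without covariates (Models 1A, 2A) and with covariates Z (Models 1B, 2B). Z includes receipt of the 2018-2019 seasonal vaccine. The adjusted results go into Tables 68-71 and 76-79; the title of Table 68 ends "Adjusted for Baseline Covariates, Per Protocol Population (N=X".

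The footnote under Tables 56, 68 and 76 reads "Note: Receipt of 2018-2019 vaccine is counted at any timepoint prior to receipt of the second study vaccination". SAP 6.4 agrees, planning on "independently assessing subject receipt of 2018-2019 seasonal vaccine (did not receive/received) prior to the second dose of study vaccine", and so does SAP 9.1: "receipt of seasonal vaccine for the current season (2018-2019; considered up to receipt of study dose 2".

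On timing, SAP 4.4.5 states "The first vaccination for all subjects takes place on the day of randomization". Dose 2 follows at 21-28 days in Groups 1 and 4. In Groups 2, 3, 5 and 6 it follows about 120 days later ("protocol defined window of 113-134 days post first vaccination").

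Protocol 5.1.2 excludes anyone who has "Received or plan to receive a licensed, seasonal IIV within 21 days before or after each study vaccination" (criterion 20). For live vaccines, criterion 18 bars those who "plan to receive a licensed, live vaccine within 30 days before or after each study vaccination". Protocol 5.2.3 lists no longer meeting eligibility criteria among the reasons dose 2 is not given.

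**The concern.** A covariate that can change after randomisation is not a baseline covariate. Here the time during which it can change is itself fixed by Interval, one of the three treatment variables in the model. Someone given seasonal vaccine 60 days after dose 1 is coded as a recipient in a 4-month arm and as a non-recipient in a 21-day arm.

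Whether 21 days or 4 months is the better interval is a stated question of the trial. Adjusting for a variable that Interval can influence may move the Interval coefficient away from the total effect of schedule, which is the comparison randomisation protects. A reader of a table headed as baseline-adjusted would not expect that. The same coding defines the strata of Tables 56-63, and baseline Tables 19 and 21 also display the variable.

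**Working it through.** **Dose gaps.** Protocol 8.2.7 sets dose 2 at Day 22 (+7) or Day 121 (-7/+14). Dose 1 is Day 1, so Day n is n - 1 days later. The gaps are 21-28 and 113-134 days, matching SAP 4.4.5.

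**Permitted between-dose days.** With gap D, seasonal IIV on day d after dose 1 is allowed if d > 21 and D - d > 21. That gives max(0, D - 43) days.
- D = 21 or 28: 0 days.
- D = 113: 113 - 43 = 70 days. D = 134: 134 - 43 = 91 days.
- If the boundary days are allowed, the count is max(0, D - 41): still 0, against 72-93.
- Live vaccine, 30-day bar, max(0, D - 61): 0, against 52-73.

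In Groups 1 and 4, between-dose receipt followed by dose 2 can therefore arise only through a deviation. The per-protocol 14-day rule for inactivated vaccine is not used here, because its reach over seasonal IIV is unclear: exclusion 19 has the same window and carves seasonal IIV out.

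**Assumed inputs.** The documents give no enrolment dates, uptake or association with titre. Let p0 be the share vaccinated before Day 1 (20-40%), and u the share of the rest vaccinated between doses in the 4-month arms (5-40%). Let g = 0.5 residual SD be the difference in log titre. Assume no direct Interval effect and 27 per arm. Then p1 = p0 + (1 - p0)u and v = p(1 - p).

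- *Share of the Received stratum in a 4-month column vaccinated after Day 1:* (p1 - p0)/p1. In the 21-day columns it is 0 apart from deviations.
- *Case A, takers differ by a fixed trait and the vaccine does nothing.* The shift in the adjusted Interval effect is -g·k·(1 - p0)·u, with k = [2·v0·(1 - u) + 4·v1]/(2·v0 + 4·v1). A Day 1 covariate gives no shift.
- *Case B, the seasonal vaccine itself changes titre.* Adjusting for receipt up to dose 2 gives 0, the direct effect. A Day 1 covariate gives g·(1 - p0)·u, the total effect of schedule, as does the unadjusted model.

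| p0 | u | p1 | Received after Day 1 | k | Case A shift (SD, absolute) | Case B total effect (SD) |
|---|---|---|---|---|---|---|
| 0.2 | 0.05 | 0.24 | 17% | 0.985 | 0.020 | 0.020 |
| 0.2 | 0.20 | 0.36 | 44% | 0.948 | 0.076 | 0.080 |
| 0.2 | 0.40 | 0.52 | 62% | 0.903 | 0.145 | 0.160 |
| 0.4 | 0.05 | 0.43 | 7% | 0.984 | 0.015 | 0.015 |
| 0.4 | 0.20 | 0.52 | 23% | 0.935 | 0.056 | 0.060 |
| 0.4 | 0.40 | 0.64 | 38% | 0.863 | 0.104 | 0.120 |

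For example, with p0 = 0.2 and u = 0.4: k = (0.192 + 0.9984)/(0.32 + 0.9984) = 0.903, and 0.5 × 0.903 × 0.8 × 0.4 = 0.145. If u or g is zero, every shift is zero. The sign in Case A is opposite to that of g.

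**Scale.** In the main-effects form the Interval contrast is roughly 54 against 54, so its standard error is about √(1/54 + 1/54) = 0.192 SD. Simulation of 27 per arm gave 0.193-0.202, and 0.273-0.281 with the interactions written in SAP 8.3.2. Simulated mean shifts in Case A agreed with the formula within 0.004 SD.

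**Season pairing.** SAP 8.3.2 and the shells pair 2016-2017 with 2017-2018 for prior seasons. SAP 6.4 pairs 2016-2017 with 2018-2019. SAP 8.3.2 says Z is defined in 6.4, so the slip sits in the rule that governs the model. Taken literally, it drops 2017-2018 and counts 2018-2019 twice.

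**The case against.** The dose 2 cut-off is deliberate and open: two SAP sections and three footnotes state it, and the model row is labelled as the concurrent season, apart from prior seasons. That stands; nothing is concealed, and what conflicts is the table title.

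Receipt before dose 2 can also be a sensible exposure for an outcome measured after dose 2. In Case B it isolates the direct effect of the interval, while a Day 1 covariate leaves seasonal vaccination inside the Interval estimate. This stands too. The two codings answer different questions, and the SAP does not say which it wants.

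A reader might infer that the planned adjustment biases the Interval result, or that a Day 1 covariate always restores a valid test of no direct effect. The documents support neither. Both inferences need Case A, together with uptake and an association that no section reports.

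**Conclusion.** The point holds, as a minor one. The day counts (0 against 70-91) and the mislabelling follow directly from the documents. The effect on estimates is conditional: if between-dose uptake occurs and is associated with titre, Models 1B and 2B need not estimate the total effect of schedule, and like-named strata in Tables 56-63 are not comparable between 21-day and 4-month columns. Tables 19 and 21 could carry post-randomisation receipt, and Table 21 could show a difference that the schedule created.

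Size and direction are unknown. Case A gives about 0.015-0.145 SD over 5-40% uptake, always under one standard error; the upper end rests on an uptake for which the documents give no support.

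A reader might go further and doubt the trial's interval findings as a whole. That does not follow: the regressions are exploratory, Models 1A and 2A report Interval without this covariate, the primary mITT summaries do not use it, and comparisons within a column of Tables 56-63 are not affected by Interval.

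**What to change.** - Define 2018-2019 receipt at Day 1 before dose 1 in Models 1B and 2B, Tables 56-63, and baseline Tables 19 and 21. State that the Interval estimate is then the total effect of schedule.
- Keep the up-to-dose-2 version as a labelled sensitivity analysis that is not called baseline.
- Report between-dose seasonal vaccination by group.
- Correct the pairing in SAP 6.4 to 2016-2017 and/or 2017-2018.

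The cost is SAP wording, shell footnotes and the added displays. No new data are needed: receipt is recorded at screening or Day 1 (Protocol 8.1.1, 8.1.3), enters the enrolment stratum (5.2.1), and later receipt is solicited separately (6.6). The downside is that the direct-effect question moves to the sensitivity analysis.
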